10.4. Appendix 4: Treatment Phases

10.4.1. Treatment Phases (Adverse Events)

Adverse events will be classified according to time of occurrence relative to the first and last dose of mepolizumab within specific study parts.

Treatment Phase	Definition
Pre-Treatment	AE Onset Date & time < First Part A dose of mepolizumab If mepolizumab treatment is never started then all AEs will be classified as pre-treatment.
On-Treatment (Part A)	First Part A dose of mepolizumab ≤ AE Onset Date & time ≤ Last Part A dose of mepolizumab + 28 days If an AE start date is missing or partial then the AE will be considered on-treatment unless there is evidence to the contrary (e.g. month/year of onset date is present and is earlier than the month/year of First Part A dose of mepolizumab).
Post-treatment (Part A)	For subjects entering Part B: Last Part A dose of mepolizumab + 28 days < AE Onset Date & time < First dose of Part B mepolizumab For subjects not entering Part B: Last Part A dose of mepolizumab + 28 days < AE Onset Date & time ≤ Visit 8 (Week 20) visit date
On-Treatment (Part B)	First dose of Part B mepolizumab ≤ AE Onset Date & time ≤ Last Part B dose of mepolizumab + 28 days If an AE start date is missing or partial then the AE will be considered on-treatment unless there is evidence to the contrary (e.g. month/year of onset date is present and is earlier than the month/year of First Part B dose of mepolizumab).
Post-treatment (Part B)	AE Onset Date & time > Last Part B dose of mepolizumab + 28 days
Onset Time Since 1 st Dose (Days)*	If Treatment Start Date > AE Onset Date = AE Onset Date - First Part A dose of mepolizumab If Treatment Start Date ≤ AE Onset Date = AE Onset Date - First Part A dose of mepolizumab + 1 If Treatment Start Date or AE Onset Date is missing = missing.
Duration (Days)	AE Resolution Date – AE Onset Date + 1
Drug-related	If relationship is marked 'YES' on Inform/eCRF OR value is missing.
* Note: will be derived as time since 1 st dose of mepolizumab utilising the First Part A dose of mepolizumab for both study parts A and B	

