4.6.1. Risk Assessment

Table 1 Assessment of Risk

Potential Risk of Clinical Significance	Data/Rationale for Risk	Mitigation Strategy
Investigational Product (IP) SB 240563		
Risk of Systemic Allergic and Non-allergic Reactions, including Anaphylaxis and local injection site reactions	
Based on data from the completed Ph 3 program in severe eosinophilic asthma, incidence rates of systemic reactions were low and similar between mepolizumab and placebo treatment groups.
 
Acute and delayed systemic reactions, including hypersensitivity, have occurred following mepolizumab administration; most reactions have been non-serious and resolved without sequelae. These reactions generally occur within hours of administration, but in some instances had a delayed onset (i.e., days).
 
An increase in the incidence of local site reactions was observed with SC administration of mepolizumab compared with placebo, but the overall incidence was low. The most common symptoms associated with subcutaneous injections included: pain, erythema, swelling, itching, and burning sensation.
 
Reactions reported to date across the mepolizumab program are summarized in the IB; see 'Special Warnings and Special
	
Daily monitoring of serious adverse events (SAEs) by Serious Adverse Events (SAE) Coordinator (project Medical Monitor); regular systematic review of adverse event (AE)/SAE data from ongoing studies by a GSK safety review team.
 
Specific case report form (eCRF) pages utilized for targeted collection of reactions data.
 
Use of Joint NIAID/FAAN 2nd Symposium on Anaphylaxis to collect data on reports of anaphylaxis (Appendix 9: Anaphylaxis Criteria).
 
In addition to normal institutional practices, subjects will be observed for a minimum of 60 minutes in the clinic following each injection up-to and including Visit 4. From Visit 9 onwards, monitoring post-injection should be according to the standard procedure at each site.

Potential Risk of Clinical Significance	Data/Rationale for Risk	Mitigation Strategy
	Precautions for Use' section located in Section 6 titled 'Summary of Data and Guidance for the Investigator'.	

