 2. For subjects who had a positive anti-mepolizumab antibody response at the 12 week post-last-dose follow-up assessment (Visit 8) (or last study visit at which immunogenicity was assessed if the Follow-up (Visit 8) immunogenicity sample is not available) an attempt will be made to obtain a serum sample for anti-mepolizumab antibodies at least 4 months after the last dose of study drug in Part A or upon completion of Part A, whichever is later.
 3. Exit visit should be performed as close as possible to the planned week 12 visit date.
 4. Therapy history to include a detailed review of prior biologics received for treatment of asthma, including prior investigational anti-IL5 or anti-IL13 preparations.
 5. During the treatment period, all lab samples and procedures should be obtained prior to study treatment administration.
 6. A positive Hepatitis B Surface Antigen and Hepatitis C antibody is exclusionary
 7. This immunogenicity sample must always be collected 12 weeks (\pm 7 days) post-last-dose of study treatment; therefore, for subjects who withdraw from study treatment early, this sample must be collected 12 weeks (\pm 7 days) after their confirmed last dose of study treatment (i.e., prior to Visit 8). In the event that this sample collection date coincides with an Early Withdrawal Visit, only one immunogenicity sample should be collected.
 8. Visit 8 to be performed 12 weeks post last dose. For subjects continuing into the long-term extension phase Part B, Visit 9 should be conducted on the same day as Visit 8 once all of the visit 8 assessments have been completed. Assessments performed at Visit 8 that are also listed for Visit 9 should not be duplicated if Visit 8 and Visit 9 are performed on the same day.

Table 4 Time and Events Table Long-Term Safety / Pharmacodynamic Phase (Part B)

Procedure	Eligibility Check / First Dose	Treatment Period													Exit Visit	Follow-up ³	Early Withdrawal
Visit	9	10	11	12	13	14	15	16	17	18	19	20	21	22	23		
Week of Study (visit window \pm 5 days)	20	24	28	32	36	40	44	48	52	56	60	64	68	72	80		
Subject Screen																	
Informed consent	X ¹																
Inclusion and exclusion criteria	X ¹																
Safety Assessments																	
Concomitant medications	X	X	X	X	X	X	X	X	X	X	X	X	X	X	X	X	
Hematology (including eosinophils) ²	X			X			X			X			X	X	X	X	
Clinical Chemistry ²	X			X			X			X			X	X		X	
12-lead ECG														X		X	
Vital signs	X	X	X	X	X	X	X	X	X	X	X	X	X	X	X	X	

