8. SECONDARY ANALYSES

8.1. Secondary and Exploratory Analyses

Table 7 provides an overview of the planned analysis of secondary and exploratory endpoints with further details of data displays being presented in Appendix 10: List of Data Displays.

All safety analyses are detailed within Section 8.2.

Table 7 Overview of Planned Secondary and Exploratory Analyses

Endpoint / Parameter/Display Type]	Raw Data								Change from Baseline							
	Stats Analysis			Summary		Individual			Stats Analysis			Summary		Individual		
	T	F	L	T	F	F	L	T	F	L	T	F	F	L		
Secondary Endpoints																
Part A																
Body-weight-adjusted clearance				Y												
ACQ-7 score				Y							Y	Y				
C-ACT score				Y							Y	Y				
Part B																
Blood Eosinophil Count				Y	Y		Y				Y ^[1]	Y ^[1]				
Exploratory Endpoints																
Part A																
ACQ-7 responder/non-responder category											Y					
ACQ-5 score				Y							Y	Y				
ACQ-5 responder/non-responder category											Y					
FEV ₁				Y							Y	Y				
Overview of Exacerbations				Y												
Exacerbations (on-treatment) (Week 0 – Week 12)				Y												
Exacerbations (on- and post-treatment) (Week 0 – Week 20)				Y			Y									
Time to first exacerbation (Week 0 – Week 20)				Y ^[2]								Y ^[2]				
Total IgE				Y							Y ^[1]					
Total IL-5				Y			Y				Y ^[1]	Y ^[1]				
PK Plasma Concentrations (Observed and Predicted)					Y ^[3]	Y ^[4]										
PK model goodness of fit test/plots	Y	Y														

Endpoint / Parameter/Display Type]	Raw Data							Change from Baseline						
	Stats Analysis			Summary		Individual		Stats Analysis			Summary		Individual	
	T	F	L	T	F	F	L	T	F	L	T	F	F	L
PKPD Plasma Concentrations (Observed and Predicted)					Y ^[3]	Y ^[4]								
PKPD model goodness of fit test/plots	Y	Y												
Part B														
ACQ-7 score				Y							Y			
ACQ-7 responder/non-responder category											Y			
ACQ-5 score				Y							Y			
ACQ-5 responder/non-responder category											Y			
C-ACT score				Y							Y			
FEV ₁				Y							Y			
Overview of Exacerbations				Y										
Exacerbations (on-treatment) (Week 20 – Week 72)				Y			Y							
Time to first exacerbation (Week 20 –Week 72)				Y ^[2]										

NOTES :

- T = Table, F = Figure, L = Listing, Y = Yes display generated.
- Stats Analysis = Represents TFL related to any formal statistical analyses (i.e. modelling) conducted.

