8.2.1.1. Adverse Events of Special Interest

Adverse events of special interest (AESIs) are adverse events associated with the identified and potential risks of mepolizumab. AESIs of anaphylaxis reactions, systemic reactions, and local injection site reactions are collected via targeted eCRF within the

study. Events captured on the eCRF as systemic reactions will be further categorized as allergic/hypersensitivity reactions or non-allergic reactions. Events with preferred terms such as injection related reaction or administration related reaction will be considered non-allergic reactions. All remaining events will be considered allergic/hypersensitivity reactions.

AESIs of opportunistic infections, malignancies, serious CVT events and serious ischemic events will be identified from a list of relevant preferred terms maintained within a project level reference dataset created based on the MedDRA dictionary available at the time of database freeze for this study, further details of how relevant preferred terms are identified are given in the Program Safety Analysis Plan (PSAP).

Separate summary tables showing the number and percent of subjects with each type of AESI, broken down by preferred term will be created. Information will be reported as part of the standard AE tables for AESIs of infections, serious infections, neoplasms, cardiac disorders and serious cardiac disorders.

For each type of AESI a profile summary table will be produced containing information which would include, but not be limited to, the number of occurrences of the event, event characteristics, time to onset, intensity, outcome and action taken.

A listing of any subjects with systemic events identified by the investigators as meeting the criteria for anaphylaxis as outlined by the 2006 Joint National Institute of Allergy and Infectious Disease/Food Allergy and Anaphylaxis Network Second Symposium on Anaphylaxis [[Sampson, 2006](#)] will be provided.

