10.4.2. Treatment Phases (Exacerbations)

Exacerbation data will be classified according to time of occurrence/assessment relative to the first and last dose of mepolizumab and the participation of subjects within to specific study parts (as dictated by attendance dates of specific visits).

Treatment Phase	Definition
Pre-Treatment	Exacerbation Onset Date & time < First Part A dose of mepolizumab If mepolizumab treatment is never started then all exacerbations will be classified as pre-treatment.
On-Treatment (Part A)	Subjects completing Part A: First Part A dose of mepolizumab ≤ Exacerbation Onset Date & time ≤ Visit 6 (Week 12) visit date Subjects discontinuing study treatment/withdrawing early from Part A: First Part A dose of mepolizumab ≤ Exacerbation Onset Date & time ≤ Earliest of (1) Last Part A dose of mepolizumab + 28 days or (2) Early Withdrawal visit date
Post-treatment (Part A)	Subjects completing Part A and entering Part B: Visit 6 (Week 12) visit date < Exacerbation Onset Date & time < First dose of Part B mepolizumab Subjects completing Part A and not entering Part B: Visit 6 (Week 12) visit date < Exacerbation Onset Date & time ≤ Visit 8 (Week 20) visit date Subjects discontinuing study treatment/withdrawing early from Part A: Earliest of (1) Last Part A dose of mepolizumab + 28 days or (2) Early Withdrawal visit date < Exacerbation Onset Date & time ≤ Visit 8 (Week 20) visit date
On-Treatment (Part B)	Subjects completing Part B: First Part B dose of mepolizumab ≤ Exacerbation Onset Date & time ≤ Visit 22 (Week 72) visit date Subjects discontinuing study treatment/withdrawing early from Part B: First Part B dose of mepolizumab ≤ Exacerbation Onset Date & time ≤ Earliest of (1) Last Part B dose of mepolizumab + 28 days or (2) Early Withdrawal visit date
Post-treatment (Part B)	Subjects completing Part B: Exacerbation Onset Date & time > Visit 22 (Week 72) visit date Subjects discontinuing study treatment/withdrawing early from Part B: Exacerbation Onset Date & time > Earliest of (1) Last Part B dose of mepolizumab + 28 days or (2) Early Withdrawal visit date

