Onset Time Since 1st Dose (Days)*	If Treatment Start Date > Exacerbation Onset Date = Exacerbation Onset Date - First Part A dose of mepolizumab If Treatment Start Date ≤ Exacerbation Onset Date = Exacerbation Onset Date - First Part A dose of mepolizumab + 1 If Treatment Start Date or AE Onset Date is missing = missing.
Duration (Days)	Exacerbation Resolution Date – Exacerbation Onset Date + 1
* Note: will be derived as time since 1 st dose of mepolizumab utilising the First Part A dose of mepolizumab for both study parts A and B	

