10.10.3.2. Efficacy Tables

No.	Population	IDSL / TST ID / Example Shell	Title	Programming Notes	Deliverable [Priority]
Blood Eosinophil Count					
2.25.	PDe		Summary of Blood Eosinophil Count (Part B)	Log transformed with geometric mean, include ratio to baseline See format of Efficacy Table 2.73 (200862 'final' reporting effort) To also include 95% CIs by visit	SAC
Asthma Control Questionnaire					
2.26.	PDo		Summary of ACQ-7 Score (Part B)	See format of Efficacy Table 2.34 (200862 'final' reporting effort) To also include 95% CIs by visit	SAC
2.27.	PDo		Summary of 0.5 Point or More Reduction in ACQ-7 Score from Baseline (Part B)	See format of Efficacy Table 2.41 (200862 'final' reporting effort). Note: Logistic regression to not be included and Odds Ratio to not be shown	SAC
2.28.	PDo		Summary of ACQ-5 Score (Part B)	See format of Efficacy Table 2.34 (200862 'final' reporting effort) To also include 95% CIs by visit	SAC
2.29.	PDo		Summary of 0.5 Point or More Reduction in ACQ-5 Score from Baseline (Part B)	See format of Efficacy Table 2.41 (200862 'final' reporting effort). Note: Logistic regression to not be included and Odds Ratio to not be shown	SAC

No.	Population	IDSL / TST ID / Example Shell	Title	Programming Notes	Deliverable [Priority]
Childhood Asthma Control Test (C-ACT)					
2.30.	PDo		Summary of C-ACT Score (Part B)	See format of Efficacy Table 2.34 (200862 'final' reporting effort) To also include 95% CIs by visit	SAC
FEV1					
2.31.	PDo		Summary of FEV ₁ (Part B)	See format of Efficacy Table 2.27 (200862 'final' reporting effort) To also include 95% CIs by visit	SAC
Asthma Exacerbations					
2.32.	PDo		Overview of Asthma Exacerbations (Part B)	See format of Efficacy Table 2.61 (200862 'final' reporting effort).	SAC
2.33.	PDo		Summary of Frequency of Exacerbations (Week 20 –Week 72) (Part B)	See format of Efficacy Table 2.62 (200862 'final' reporting effort)	SAC
2.34.	PDo		Summary of Time to First Asthma Exacerbation (Part B)	See format of Efficacy Table 2.68 (200862 'final' reporting effort)	SAC

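### The SAP's only onset-time variable counts from the first Part A dose, so it does not show time since the triggering injection, and the Part B time-to-first-exacerbation table has no stated day 0

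*SAP*

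**What the plan says.** SAP 10.4.1 defines one onset time for adverse events, counted in days since the first dose. A footnote says it is derived "utilising the First Part A dose of mepolizumab for both study parts A and B". SAP 10.4.2 repeats the footnote for exacerbations and gives the formula "Exacerbation Onset Date - First Part A dose of mepolizumab + 1" for events on or after the start of treatment.

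SAP 8.2.1.1 requires a profile table for each type of adverse event of special interest, with content that includes "time to onset, intensity, outcome and action taken". It does not name the dose from which onset is measured. The Part B display list repeats these profiles for systemic, local injection-site and anaphylaxis events. Protocol 4.6.1 says of systemic reactions: "These reactions generally occur within hours of administration, but in some instances had a delayed onset".

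For exacerbations, SAP Table 7 lists the Part B item "Time to first exacerbation (Week 20 –Week 72"), to be given as Kaplan-Meier estimates. The output is Table 2.34, "Summary of Time to First Asthma Exacerbation (Part B"). No day 0 and no censoring rule is given for it. The Part B on-treatment window for subjects who complete is "First Part B dose of mepolizumab ≤ Exacerbation Onset Date & time ≤ Visit 22 (Week 72) visit date".

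**The concern.** For an injection reaction, the informative interval runs from the injection that preceded it. The protocol's own risk assessment describes timing that way, in hours and sometimes days after a dose. A count of days since Week 0 mixes that interval with the number of doses already given. Safety is the primary objective of Part B, and from Visit 9 the fixed 60-minute observation gives way to each site's own procedure (Protocol 4.6.1). A summary of when reactions occur after each dose would therefore be useful, and the defined variable does not supply it.

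For Table 2.34 the risk is a programming ambiguity. The display is labelled as a Part B interval, yet the only exacerbation time variable in the SAP starts 20 weeks earlier. Two programmers could follow the text in good faith and produce tables whose time axes differ by about 140 days.

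**Working it through.** **Inputs**
- Onset formula: onset date − first Part A dose + 1 (SAP 10.4.1 and 10.4.2).
- Part A doses: Weeks 0, 4 and 8 (Protocol Table 3).
- Part B doses: Weeks 20, 24, …, 68, which is 13 doses (Protocol Table 4). The first falls on the Visit 8 day, since "Visit 9 should be conducted on the same day as Visit 8 once all of the visit 8 assessments have been completed" (Protocol section 7, Table 3 footnote).
- End of Part B treatment: Visit 22, Week 72.
- Part B visit window: ±5 days.

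**Check against the plan's own figure.** 72 − 20 = 52 weeks (364 days). This reproduces the protocol's stated 52 weeks of Part B treatment.

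**Offset.** 20 × 7 = 140 days, or 135 to 145 days with the ±5-day window.

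**Same-day reactions.** A reaction on the day of the dose at Week k gets onset 7k + 1:

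| Dose | Weeks | Onset on the SAP clock | Onset from most recent dose |
|---|---|---|---|
| Part A, doses 1 to 3 | 0, 4, 8 | days 1, 29, 57 | day 1 each time |
| Part B, doses 1 to 13 | 20, 24, …, 68 | days 141, 169, …, 477 | day 1 each time |

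A reaction 27 days after the Week 20 dose gets 140 + 27 + 1 = day 168. A reaction on the day of the Week 24 dose gets day 169. The two values are adjacent, although one reaction came nearly four weeks after an injection and the other on the same day.

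Moving the origin to the first Part B dose would not cure this. Same-day reactions to Part B doses 2 and 3 would then get days 29 and 57, exactly as in Part A.

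**Table 2.34, if it used the Week 0 variable.**
- Part B treatment would span days 141 to 505 instead of days 1 to 365. Every subject would be event-free to day 140 by construction.
- An estimate read at day 364 would cover 364 − 140 = 224 days, which is 32 weeks of Part B.
- To show the size, assume a constant exacerbation rate r per year, so that cumulative incidence is 1 − exp(−r × t / 365.25). The documents give no Part B rate, so the rates below are assumptions.

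| Assumed r | t = 364 days of Part B | Read at day 364 on the Week 0 clock (t = 224) |
|---|---|---|
| 0.5 | 39% | 26% |
| 1 | 63% | 46% |
| 2 | 86% | 71% |

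With a constant offset, the order of events, the risk sets and the final estimate do not change. Only the time labels move.

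**The case against.** The strongest reply is that nothing is lost. The date and time of each injection go into the eCRF (Protocol 6.3). Part B treatment data are listed (Listing 57), and systemic, local and anaphylaxis events each have their own listing (Listings 65 to 67). SAP 10.5.3 says listings show time relative to dosing, although it does not say which dose. A reader might infer from the footnote that Part B reactions cannot be related to an injection at all. The documents do not support that: the interval follows by subtracting the dose date. The content of the profile tables is also left open-ended, and their layouts are taken from another study's outputs, so whether they show time since the latest injection cannot be checked here.

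Time since first-ever exposure is also a legitimate measure for a long-term safety objective and for slow events such as malignancy. It matches the single pre-treatment baseline used for both parts.

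On exacerbations, a reader might infer that a Part B Kaplan-Meier curve begins about 140 days too early. That is not supported either. The only Kaplan-Meier figure listed is for Part A (Figure 2.22); the Part B efficacy figures are both of eosinophils. The SAP does not say that Table 2.34 uses the Week 0 variable, and both its Week 20 to 72 label and the Part B on-treatment window point to a Part B start. The protocol's exploratory endpoint is the incidence of exacerbations, which does not depend on this variable, and no hypothesis is tested.

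All of this stands, and it limits the point. It does not supply a defined variable for time since the most recent dose, or a stated day 0 and censoring rule for Table 2.34.

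**Conclusion.** The point holds as a low-cost improvement to the SAP. The single defined onset-time variable does not show the interval from the triggering injection. This is true in both parts: same-day reactions get days 29 and 57 for Part A doses 2 and 3, and days 141 to 477 in Part B. It is a gap in the planned summaries, not a loss of data. It rests on the assumption that the time to onset in the profile tables is the variable of SAP 10.4.1, the only candidate in the visible text.

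For Table 2.34, the defect is that day 0 and censoring are unstated while the only defined exacerbation time starts at Week 0. The shift of about 140 days, with 52 weeks on the axis covering about 32 weeks of Part B, is conditional on that variable being used. The percentages above also rest on assumed constant rates. All the displays concerned are descriptive, so no test, sample size or primary conclusion changes.

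**What to change.** 1. For systemic, local injection-site and anaphylaxis events in both parts, derive time since the most recent dose, in hours where the onset time is recorded and otherwise in days. Name it as the time to onset summarised in those profile tables.
2. For Table 2.34, state that day 0 is the first Part B dose, and state the censoring rule. The end of the Part B on-treatment window in SAP 10.4.2 is a natural choice, because it already covers both completers and subjects who stop early.
3. Keep time since the first-ever dose as an additional measure in the listings.

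The cost is a few lines of SAP text and simple derivations from dates and times already collected. No visit, assessment or data item is added.

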10.4.2. Treatment Phases (Exacerbations)

Exacerbation data will be classified according to time of occurrence/assessment relative to the first and last dose of mepolizumab and the participation of subjects within to specific study parts (as dictated by attendance dates of specific visits).

Treatment Phase	Definition
Pre-Treatment	Exacerbation Onset Date & time < First Part A dose of mepolizumab If mepolizumab treatment is never started then all exacerbations will be classified as pre-treatment.
On-Treatment (Part A)	Subjects completing Part A: First Part A dose of mepolizumab ≤ Exacerbation Onset Date & time ≤ Visit 6 (Week 12) visit date Subjects discontinuing study treatment/withdrawing early from Part A: First Part A dose of mepolizumab ≤ Exacerbation Onset Date & time ≤ Earliest of (1) Last Part A dose of mepolizumab + 28 days or (2) Early Withdrawal visit date
Post-treatment (Part A)	Subjects completing Part A and entering Part B: Visit 6 (Week 12) visit date < Exacerbation Onset Date & time < First dose of Part B mepolizumab Subjects completing Part A and not entering Part B: Visit 6 (Week 12) visit date < Exacerbation Onset Date & time ≤ Visit 8 (Week 20) visit date Subjects discontinuing study treatment/withdrawing early from Part A: Earliest of (1) Last Part A dose of mepolizumab + 28 days or (2) Early Withdrawal visit date < Exacerbation Onset Date & time ≤ Visit 8 (Week 20) visit date
On-Treatment (Part B)	Subjects completing Part B: First Part B dose of mepolizumab ≤ Exacerbation Onset Date & time ≤ Visit 22 (Week 72) visit date Subjects discontinuing study treatment/withdrawing early from Part B: First Part B dose of mepolizumab ≤ Exacerbation Onset Date & time ≤ Earliest of (1) Last Part B dose of mepolizumab + 28 days or (2) Early Withdrawal visit date
Post-treatment (Part B)	Subjects completing Part B: Exacerbation Onset Date & time > Visit 22 (Week 72) visit date Subjects discontinuing study treatment/withdrawing early from Part B: Exacerbation Onset Date & time > Earliest of (1) Last Part B dose of mepolizumab + 28 days or (2) Early Withdrawal visit date
Onset Time Since 1st Dose (Days)*	If Treatment Start Date > Exacerbation Onset Date = Exacerbation Onset Date - First Part A dose of mepolizumab If Treatment Start Date ≤ Exacerbation Onset Date = Exacerbation Onset Date - First Part A dose of mepolizumab + 1 If Treatment Start Date or AE Onset Date is missing = missing.
Duration (Days)	Exacerbation Resolution Date – Exacerbation Onset Date + 1
* Note: will be derived as time since 1 st dose of mepolizumab utilising the First Part A dose of mepolizumab for both study parts A and B	

